3.1 Type/Design of Trial

This will be a 3-week, multicenter, randomized, double-blind, placebo-controlled trial of brexpiprazole in subjects diagnosed with bipolar I disorder (current manic episode with or without mixed features) according to the *Diagnostic and Statistical Manual of Mental Disorders, Fifth Edition* (DSM-5; updated terminology replaces “mixed episodes” with the descriptor of “mixed features”). The total duration of the trial is up to 8 weeks, including screening, double-blind treatment, and follow-up. See [Figure 3.1-1](#) for a schematic of the trial design.

The trial will be organized as follows:

Screening Phase: The screening period will begin after written informed consent has been obtained and will take place between Day -14 and Day -1 prior to randomization. Hospitalization will begin with the signing of the informed consent form (ICF) for subjects who are not already hospitalized at the time of the initial screening visit. The purpose of the screening period is to assess eligibility criteria and to washout prohibited concomitant medication. Subjects will be between 18 and 65 years of age, inclusive, at the time of screening, will have a diagnosis of bipolar I disorder, and will be experiencing a manic episode with or without mixed features as defined by the DSM-5 criteria. An interactive web response system (IWRS) or equivalent will be used to obtain an

Protocol 331-201-00080

identification (ID) number for each subject with documented consent. Although the screening period will continue up to administration of the first dose of investigational medicinal product (IMP), screening procedures should be initiated with a sufficient amount of time allotted in order to obtain laboratory results and electrocardiogram (ECG) results from the central reader prior to randomization. The sponsor reserves the right to utilize external quality oversight methods to ensure the validity of diagnosis, severity of illness, and other factors determining appropriateness of subject selection.

All subjects must agree to discontinue all prohibited medications during the screening period in order to meet the protocol-specified washout periods.

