3.4 Eligibility Criteria

3.4.1 Informed Consent

Informed consent will be freely obtained from all subjects. The ICF will be approved by the same institutional review board or independent ethics committee (IRB/IEC) that approves this protocol.

Each ICF will comply with the ICH (International Conference on Harmonisation) Good Clinical Practice (GCP) Guideline¹¹ and local regulatory requirements. The investigator will ensure that the sponsor or its designee reviews and authorizes any written site-specific ICF used in the trial before submission to the IRB/IEC.

Investigators may discuss trial availability and the possibility for entry with a potential subject without first obtaining consent. However, informed consent must be obtained and documented before initiation of any procedures that are performed solely for the purpose of determining eligibility for this trial, including withdrawal from current medication(s).

Potential subjects are free to refuse entry into the trial, or withdraw from the trial at any time, without justification, and there will be no consequences to their further care.

Prospective trial participants will be provided with controlled access to the electronic informed consent application by site staff. When the site staff and the participant agree that the participant has enough information to make an informed decision to participate, the participant will electronically sign the electronic ICF application and an electronic date and time stamp will be applied to the signature. The participant will be given a printed, signed copy of the consent form. Any other parties required by the IRB/IEC (trial site staff, witnesses, or legally authorized representative) are also required to sign electronically and these signatures will be stored with the electronic ICF in accordance with the ICH GCP Guideline and local regulatory requirements/guidelines. These

Protocol 331-201-00080

signatures cannot be altered, removed, or copied. In the event electronic ICFs are not allowed per local or country regulations, a paper consent will be utilized.

Subjects may be asked to sign additional ICFs if the protocol is amended and the changes to the protocol results in additional information that needs to be provided to the subjects, so that they can make a knowledgeable and voluntary decision on trial participation.

CCI

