3.4.3 Exclusion Criteria

Subjects will be excluded if they meet any of the exclusion criteria in [Table 3.4.3-1](#).

Table 3.4.3-1 Exclusion Criteria	
	Sex and Reproductive Status
1.	Sexually active males or WOCBP who do not agree to practice 2 different methods of birth control or remain abstinent during the trial and for 30 days after the last dose of IMP. If employing birth control, 2 of the following precautions must be used: vasectomy, tubal ligation, vaginal diaphragm, intrauterine device, birth control pill, birth control implant, birth control depot injection, condom with spermicide, or sponge with spermicide.
2.	Females who are breastfeeding and/or who have a positive pregnancy test result prior to receiving IMP.
	Target Disease
3.	Subjects with a history of DSM-5 diagnosis other than bipolar I disorder, including schizophrenia, schizoaffective disorder, major depressive disorder, attention-deficit/hyperactivity disorder, delirium, dementia, amnestic, or other cognitive disorders. Also, subjects with borderline, paranoid, histrionic, schizotypal, schizoid, or antisocial personality disorder. All other current diagnoses must be discussed with the medical monitor.
4.	Subjects whose current manic episode has lasted for more than 4 weeks overall, or who have required hospitalization > 21 days for the current acute episode at the time of the screening visit, excluding hospitalization for psychosocial reasons.
5.	Subjects who have had initiation of, or a change in, psychotherapy for the treatment of bipolar disorder symptoms within 28 days prior to the screening visit or if it is anticipated that the subject will have a change in psychotherapy during the trial.
6.	Subjects with manic symptoms that are better accounted for by another general medical condition or direct physiological effects of a substance (eg, medications).
7.	Subjects considered unresponsive to clozapine or who are only responsive to clozapine .
8.	Subjects with bipolar I disorder who are considered resistant or refractory to treatment for manic symptoms by history.
9.	Subjects who have had electroconvulsive treatment within the past 2 months.
10.	Use of psychotropic medications (other than benzodiazepines) within 7 days of the baseline YMRS.
11.	Rapid cyclers with more than 6 episodes in the previous year.

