3.7 Trial Procedures

This trial is a phase 3, double-blind, placebo-controlled trial to investigate the efficacy, safety, and tolerability of brexpiprazole (2-4 mg/day) for the treatment of subjects with bipolar I disorder experiencing a manic episode with or without mixed features. The trial comprises a 3-week, double-blind treatment period with a 21 (\pm 2) day follow-up.

Trial assessment time points are summarized in [Table 3.7.1](#).

Protocol 331-201-00080

Table 3.7-1 Schedule of Assessments

	Screening ^a	Double-blind Treatment Phase					Follow-up ^c
	Day -14 to -1	Baseline (Day 1)	Day 4 (± 1 day)	Day 7 (± 1 day)	Day 14 (± 1 day)	Day 21/ET ^b (± 2 days)	21 (± 2) days after last dose
Screening Assessments and Randomization							
Informed Consent ^d	X						
Demographics	X						
Medical History	X						
Psychiatric History	X						
MINI	X						
Concomitant Medications ^e	X	X	X	X	X	X	X
Inclusion/Exclusion Criteria	X	X					
Randomization		X					
Efficacy Assessments							
YMRS ^f	X	X	X	X	X	X	
CGI-BP ^g		X	X	X	X	X	
CCI ^h		X	X		X	X	
Safety Assessments							
Physical Examination ⁱ	X					X	
Vital Signs ^j	X	X	X	X	X	X	
Body Weight	X					X	
12-lead ECG ^j	X	X				X	
Clinical laboratory tests (hematology, serum chemistry, urinalysis), including prolactin ^k	X					X	
HbA1c ^j	X					X	

Protocol 331-201-00080

Table 3.7-1 Schedule of Assessments

	Screening ^a	Double-blind Treatment Phase					Follow-up ^c
	Day -14 to -1	Baseline (Day 1)	Day 4 (± 1 day)	Day 7 (± 1 day)	Day 14 (± 1 day)	Day 21/ET ^b (± 2 days)	21 (± 2) days after last dose
TSH, with reflex to T4 if TSH is abnormal	X					X	
Coagulation parameters (PT, aPTT, INR) ^k	X					X	
Lithium, Valproate, Carbamazepine Levels ^l	X						
HIV, HBsAg, and anti-HCV	X						
Pregnancy Test ^m	X		X			X	
Drug Screen ⁿ	X					X	
Blood Alcohol Test ⁿ	X					X	
C-SSRS ^o	X	X	X	X	X	X	
CCl							
AEs ^p	X	X	X	X	X	X	X
CCl							
Other							
IMP dispensing ^r		X	X	X	X		
IMP accountability			X	X	X	X	

Protocol 331-201-00080

aPTT = activated partial thromboplastin time; HBsAg = Hepatitis B surface antigen; Anti-HCV = Antibodies to hepatitis C virus; INR = International Normalized Ratio; T4 = free thyroxine; TSH = thyroid-stimulating hormone.

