^jStandard 12-lead ECGs will be performed after the subject has been supine and at rest for ≥ 5 minutes prior to the ECG. A central ECG service will be utilized to review all ECGs in order to standardize interpretations for the safety analysis. In addition, ECG results will be evaluated at the investigational site to monitor safety during the trial. Any screening ECG with abnormal result(s) considered to be clinically significant should be repeated to confirm the finding(s) before excluding the subject from the trial. Subjects will be randomized based on screening ECG results from the central reader and baseline ECG results from the trial site. If the baseline ECG results from the central reader, when available, indicate a QT interval corrected for heart rate by Fridericia's formula (QTcF) ≥ 450 msec in men and ≥ 470 msec in women, unless due to ventricular pacing, at baseline, the investigator must contact the medical monitor to discuss the subject's continued participation in the trial. ECGs scheduled for the same visit as blood samples are to be completed before blood is drawn.

Protocol 331-201-00080

^kSubjects must be fasting for a minimum of 8 hours prior to blood draws for screening laboratory assessments, if at all possible. If fasting blood samples are not feasible at screening, nonfasting blood samples may be obtained initially for determining eligibility for the trial. Clinical laboratory tests must be drawn after a minimum 8-hour fast at Day 21/ET. Vital sign and ECG assessments should be completed before any blood samples are collected.

^lIf lithium, valproate, or carbamazepine levels are outside of the listed exclusionary range, they may be reassessed prior to randomization.

^mAll positive urine pregnancy test results must be confirmed by a serum test. Subjects with positive urine and serum pregnancy test results at screening must not be enrolled. Subjects with positive urine and serum pregnancy test results during the trial must discontinue treatment and be withdrawn from the trial. Pregnancy tests can be performed at any point during the trial if pregnancy is suspected.

ⁿA urine drug screen and a blood alcohol test are required at the designated times, but either or both can be conducted at any time during the trial at the discretion of the investigator.

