3.7.1 Schedule of Assessments

3.7.1.1 Screening (Day -14 to -1)

The screening period begins after consent has been obtained. Consent should also be obtained for optional FBR for those subjects that want to participate. Although the screening period takes place between Day -14 and Day -1, subjects will participate in screening activities for a minimum of 1 day. After a subject has provided consent, sites will obtain a subject ID number for the subject by accessing the IWRS or equivalent. Screening evaluations will include the following:

- Hospitalization will begin once the subject signs the ICF for subjects who are not already hospitalized at the time of the screening visit.
- A qualified and certified rater will administer the YMRS **CCI** [REDACTED]
- An assessment of all inclusion and exclusion criteria will be made to determine the subject's eligibility for the trial.
- Demographic data will be recorded.
- A general clinical evaluation will be performed, including concurrent medical conditions, medical history over the past 2 years, and medical history beyond 2 years which is considered to be clinically relevant per the investigator's judgment.
- Psychiatric history will be recorded, including the DSM-5 diagnosis of bipolar I disorder that will be made by an adequately trained and experienced clinician and will be confirmed by the administration of the MINI.
- Medications (including those that were taken within 30 days of screening) will be recorded. In addition, all prescription and non-prescription medications taken during the trial will be recorded as concomitant medications. Details of prohibited/restricted medications are provided in [Table 4.1-1](#) and [Table 4.1-2](#).
- Washout from prohibited concomitant medications, if applicable ([Table 4.1-1](#)).
- **CCI** [REDACTED]
- The investigator (or qualified designee) who is adequately trained will complete the "Baseline/Screening" C-SSRS form to exclude subjects with a significant risk of suicidal behavior (see [Table 3.4.3-1](#)).
- A complete physical examination (including height and waist circumference) will be performed.
- Vital sign measurements (body weight, body temperature, blood pressure, and heart rate) will be recorded. Blood pressure and heart rate are to be measured in the following order: supine and standing after the subject has been in each position at least 3 minutes. See [Table 3.4.3-1](#) for exclusions based on outcome of screening vital sign measurements.

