3.7.1.2 Baseline (Day 1)

If the subject continues to be eligible for the trial after the screening period, the following procedures will be performed:

- An assessment of all inclusion and exclusion criteria will be made to confirm the subject's eligibility for the trial.
- A qualified and certified rater will administer the YMRS, CGI-BP, **CCI** [REDACTED]
[REDACTED] [REDACTED]
- The investigator (or qualified designee) who is adequately trained will complete the "Baseline/Screening" C-SSRS form.
- Vital sign measurements (body temperature, blood pressure, and heart rate) will be recorded. Blood pressure and heart rate are to be measured in the following order: supine and standing after the subject has been in each position at least 3 minutes. See [Table 3.4.3-1](#) for exclusions based on outcome of screening vital sign measurements.
- A standard 12-lead ECG will be performed after the subject has been supine and at rest for at least 5 minutes. See [Table 3.4.3-1](#) for exclusions based on ECG results.
- Adverse events and concomitant medications will be recorded.

Protocol 331-201-00080

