## 9.2 Clinical Laboratory Tests

Summary statistics for mean and mean change from baseline in the routine clinical laboratory measurements, prolactin concentrations, coagulation parameters (PT, aPTT, and INR), HbA1c, and TSH will be provided by treatment and by visit.

Potentially clinically relevant laboratory measurement test results in the double-blind treatment period will be identified for the Safety Sample and will be summarized by treatment group and listed. Criteria for identifying laboratory values of potential clinical relevance are provided in [Appendix 2](#).

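### Baselines for body weight and for fasting glucose and lipids are inconsistently defined across the protocol schedule, its footnotes and the SAP

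*Protocol*

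**What the plan says.** **Weight.** Table 3.7-1 has a separate Body Weight row, marked at Screening and Day 21/ET only. The procedure lists agree: sections 3.7.1.2 to 3.7.1.6 describe vital signs without weight, as in "Vital sign measurements (body temperature, blood pressure, and heart rate) will be recorded". Footnote i of the same table and section 3.7.3.3.2 define vital signs to include weight, and the Vital Signs row is marked at every visit from Screening to Day 21/ET. SAP 9.5.1 analyses weight change by ANCOVA with baseline as covariate, and analyses gains and losses of at least 7% by a CMH test.

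**Laboratory tests.** The row "Clinical laboratory tests (hematology, serum chemistry, urinalysis), including prolactin" is marked at Screening and Day 21/ET only, as are HbA1c and TSH. On fasting, footnote k says: "If fasting blood samples are not feasible at screening, nonfasting blood samples may be obtained initially for determining eligibility for the trial". At Day 21/ET an 8-hour fast is mandatory. SAP 9.2 plans "Summary statistics for mean and mean change from baseline in the routine clinical laboratory measurements, prolactin concentrations" and does not restrict this to fasting samples. SAP 9.2.2 counts shifts in fasting lipids and fasting glucose.

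**Baseline.** SAP 9 takes the last observation before the first dose, unless specified otherwise. The footnotes to both SAP 9.2.2 tables specify otherwise: they take baseline from Week 1.

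**Washout.** Protocol 3.1 says: "The purpose of the screening period is to assess eligibility criteria and to washout prohibited concomitant medication". Exclusion 10 bars "Use of psychotropic medications (other than benzodiazepines) within 7 days of the baseline YMRS". On the length of screening, section 3.7.1.1 says: "Although the screening period takes place between Day -14 and Day -1, subjects will participate in screening activities for a minimum of 1 day". Section 3.4.1 requires consent before medication is withdrawn for the trial.

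**The concern.** Safety and tolerability is the secondary objective, and much of its weight and metabolic evidence is change from baseline or a shift from a baseline category. Such a number can be read only if the baseline is one thing for all subjects and is comparable with the Day 21 value. Here a site can follow the protocol and have a Day 1 weight, or follow it and have only a screening weight. A glucose change can compare a nonfasting value with a fasting one. A programmer who takes the Week 1 footnote literally will find no planned sample to use. In addition, a subject still on a previous psychotropic at the screening draw may have a baseline that reflects that drug, so the later change includes its removal as well as the effect of the trial treatment.

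**Working it through.** The plan gives no figure to reproduce. The check sets the passages against each other, then does day arithmetic and one illustration.

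**1. Weight.** Under the Body Weight row and the procedure lists, the latest scheduled pre-dose weight is the screening one (Day -14 to Day -1). Under footnote i and 3.7.3.3.2 it is Day 1. There is no Day 0, so the interval from a screening day -s to Day 21 is 21 + s - 1 days, of which s precede the first dose.

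| Baseline weight | Interval to Day 21 | Pre-dose days | Share |
|---|---|---|---|
| Day -14 | 34 | 14 | 14/34 = 41% |
| Day -1 | 21 | 1 | 1/21 = 5% |
| Day 1, pre-dose | 20 | 0 | 0% |

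With the ±2-day window at Day 21, the Day -14 share runs from 14/36 = 39% to 14/32 = 44%.

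**2. Fasting status.** No draw is scheduled between Screening and Day 21/ET. A nonfasting screening sample therefore stays the last pre-dose value unless an unscheduled repeat is taken. Exclusion 17 requires a fasted retest only in subjects with non-insulin-dependent diabetes whose nonfasting glucose is at least 200 mg/dL. The documents themselves do not treat the two states as interchangeable: SAP Appendix 2 flags glucose at 100 mg/dL fasting but 200 mg/dL nonfasting. Neither SAP 9.2 nor 9.2.2 gives a rule for a nonfasting baseline.

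**3. Week 1.** SAP 9.9 defines Week 1 as Days 1 to 7. Table 3.7-1 schedules no laboratory draw in those days. Only a subject who terminates early in that week would have a scheduled-type sample, and it would be on treatment. The footnote therefore conflicts with the SAP 9 rule and, read literally, leaves nearly every subject without a metabolic baseline.

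**4. Washout (illustration; the documents give no inputs).** Work in SD units, with change-score SD 1 in the absence of washout. Let f be the share on a prior drug at the screening draw, w the shift when that drug is removed, and d the effect of brexpiprazole.

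- Mean change, brexpiprazole: d + f·w. Placebo: f·w. Difference: d.
- With f = 0.5, w = -0.5, d = 0.3: brexpiprazole 0.3 - 0.25 = +0.05; placebo -0.25; difference 0.30. With a Day 1 baseline: +0.30, 0 and 0.30.
- Over f = 0.25 to 0.75 and w = -0.2 to -1.0, each arm shifts by between 0.25 × 0.2 = 0.05 and 0.75 × 1.0 = 0.75 SD downward. The difference does not move.
- The standard error is multiplied by √(1 + f(1-f)w²): from √1.0075 = 1.004 (f = 0.25, w = -0.2) to √1.25 = 1.118 (f = 0.5, w = -1.0).
- Share with a rise above 1 SD, screening baseline: brexpiprazole ½[P(Z > 0.7) + P(Z > 1.2)] = ½(0.242 + 0.115) = 17.9%; placebo ½(0.159 + 0.067) = 11.3%. Day 1 baseline: 24.2% and 15.9%. The gap is 6.6 points instead of 8.3. A simulation of 4,000 trials with 160 per arm agrees: 17.8% vs 11.3%, and 24.2% vs 15.8%, with gaps of 6.5 and 8.4 points.

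**The case against.** The strongest reply is that washout comes before 1:1 randomisation against concurrent placebo, so both arms carry it. That stands: the between-arm difference in mean change and the weight ANCOVA are not biased by it. Randomisation is also stratified by site (Protocol 3.6), so a site's weighing practice is shared across its arms. The arm comparison of the 7% weight rows and of the shift counts remains valid too. At most the incidences are attenuated, and that rests on assumed inputs.

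Several outputs do not depend on baseline. The prolactin, glucose and lipid criteria in SAP Appendix 2 are absolute thresholds, and the metabolic syndrome criteria are post-baseline levels. SAP 9.2.2 also has rows for borderline, impaired and any-value baselines, so a subject with a raised baseline is not simply lost. SAP 9.2 already plans Day 21 means by arm. All of this stands.

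The timing argument is also fair. Screening may last one day, nothing ties the draw to consent, questionable results may be repeated, section 3.7.1.1 asks for a fasted sample, and subjects already drug-free have no washout. A nonfasting value most naturally fails to qualify for a row labelled fasting, which makes it a missing baseline rather than an inflated one. The SAP does not say so, however, and the mean changes in SAP 9.2 carry no such label.

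A reader might infer more: that weight, prolactin, TSH, glucose and lipids all have only a screening baseline, so that the safety comparison confuses removal of the old drug with the effect of the new one. The documents do not support that. Weight is contradictory rather than screening-only, and the comparison with placebo is protected. No passage gives the share of subjects on prior drugs or the size of any carry-over, and the table of pre-trial medication restrictions (Table 4.1-1) is not in the text available for this review.

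**Conclusion.** The point holds as an inconsistency of definition that should be corrected, not as a bias in the arm comparison. Three defects follow from the text alone: the passages on Day 1 weight contradict each other; a nonfasting baseline can be set against a fasting endpoint with no rule; and the Week 1 footnote matches no scheduled draw and conflicts with SAP 9. Baseline weight can be anything from a Day 1 value to one 14 days before dosing, so 0% to 41% of the change interval may precede treatment. The 41% is the Day -14 extreme.

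The washout effect is conditional. It reaches within-arm changes and shift incidences only in subjects sampled on, or just off, a prior psychotropic, and its size is unknown. The 0.05 to 0.75 SD range is an illustration under assumed inputs.

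**What to change.** 1. **Weight.** Reconcile the Body Weight row, footnote i, and sections 3.7.1.2 to 3.7.1.6 and 3.7.3.3.2 so that every subject is weighed before the first dose on Day 1. Name that value as baseline in SAP 9.5.1. Subjects are already inpatients, so the cost is close to nil.
2. **Week 1 footnote.** In both SAP 9.2.2 tables, replace it with the last value before the first dose. This is a wording change.
3. **Fasting rule.** In SAP 9.2 and 9.2.2, use only fasting baselines for changes and shift rows in fasting glucose and lipids, and report how many subjects lack one.
4. **Interpretation.** State that laboratory changes are read as brexpiprazole versus placebo. Add a supportive table split by psychotropic use in the 30 days before screening, which the protocol already records.

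The price is smaller denominators in the fasting and split rows, and one extra table. A further pre-dose fasting blood draw would remove more of the problem, but it is an added procedure and a matter of design preference. The point does not depend on it.
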